6.2 Participants

The targeted sample size for study completion is 24 Veterans, 12 per group.²⁵ Given that positive psychology web-based interventions have an average attrition rate of approximately 50% for clinical populations,²⁶ we aim to recruit and randomize 48 eligible Veterans within the initial baseline assessment to account for the expected attrition and to reach the goal of 24 Veteran completers. Specifically, "eligible" status is determined by passing the initial pre-screen over the phone, then passing the final screen for all inclusion and exclusion criteria after completion of the baseline assessment. For all Veterans who are determined eligible after the baseline appointment, one Significant Other will be recruited to complete observational measures for each Veteran. Therefore, we aim to recruit 48 eligible Veterans and 48 corresponding Significant Others. Given that participants need to verbally consent to the baseline appointment to determine final eligibility for full enrollment and randomization, it is possible that some consenting Veterans will not meet the inclusion criteria after consenting at baseline. In other words, consent does not automatically equal randomization. Any Veteran who consented but was then deemed ineligible based on the results of the baseline assessment would not be considered as contributing to the minimum sample size of 48 eligible Veterans. We anticipate that 2 out of every 3 participants is likely to be eligible after conducting a baseline appointment; therefore, we aim to obtain verbal consent from approximately 72 Veterans to meet the sample size required for eligible and enrolled Veterans. When combining the 48 Significant Others who are expected to consent after a Veteran is enrolled and randomized, we aim to recruit a total of 120 participants.

6.3 Inclusion Criteria

Veteran Participants: Veterans must meet all of the following to participate: 1) \geq 18 years of age; 2) OEF/OIF/OND Veteran enrolled in CTVHCS; 3) English-speaking and able to provide written informed consent; 4) Internet access for web-based sessions and measures; 5) Screen positively for a PTSD diagnosis based on empirically-validated cutoffs on the PTSD Checklist for DSM-5 (PCL-5;²⁷ \geq 33); 6) Screen positively for experiencing \geq 1 morally injurious event and endorse some distress (\geq 4 on any distress item) related to that event based on the Moral Injury Events Scale (MIES);²⁸ 7) Willing to complete study procedures and identify a Significant Other who will complete observational measures; and 8) Willing to be randomized.

Significant Other Participants: Significant Others must meet all of the following to participate: 1) ≥ 18 years of age; 2) Designated as a Significant Other by the Veteran participant, and the Veteran participant has provided consent for the study team to contact that potential Significant Other; 3) English-speaking; 4) Internet access for web-based observational measures; 5) Interact with the Veteran ≥ 1 time per week; and 6) Willing to complete study procedures.

6.4 Exclusion Criteria

Veteran Participants: The intent of exclusion criteria for this study is to ensure that study participants are able to provide informed consent, understand study materials, and complete study-related tasks, and for the study team to detect and provide referrals for urgent treatment of suicidality. Therefore, Veterans will be screened for the following exclusion criteria and will be excluded if any exclusion criteria are met: 1) History of severe traumatic brain injury (TBI) indicated by medical review and the Ohio State Traumatic Brain Injury Identification Method (OSU TBI-ID);²⁹ 2) Psychosis or current substance use disorder indicated by medical review and the Mini International Neuropsychiatric Interview (MINI);^{30,31} or 3) Current suicide risk based

on the Beck Depression Inventory-II (BDI-II; score of ≥ 2 on suicide item indicates risk warranting crisis intervention³²). Veterans will not be excluded if they are enrolled in other treatments, including psychotherapy or pharmacotherapy, and they will be allowed to engage in and/or initiate other treatments during the study if desired. Ineligible participants based on Exclusion Criteria 1 and 2 will be identified first in the initial medical record review (database query from the VA Corporate Data Warehouse [CDW]) and will be excluded (i.e., will not receive a mailed invitation to participate in this study). Screening for exclusion criteria will be verified during the pre-intervention assessment (i.e., at baseline) with the OSU TBI-ID, MINI, and BDI-II. The BDI-II is a 21-item self-report measure of depression symptoms, which will be used to assess for suicide risk as defined by a score of ≥ 2 on the BDI-II suicide item.³² The BDI-II suicide item evidences a moderate correlation with other scales of suicidal ideation in clinical samples and has predictive validity.³³ Follow-up risk-assessment will be provided (see Section 8.2, B.2 [Protection against risk of emotional distress] for additional details).

Significant Other Participants: None.

6.5 Recruitment

Veteran participants will be recruited through advertisement at enrollment sites, vet centers, Veteran's networks and service organizations, through in-service presentations to primary care staff. mental health staff, and other relevant VA staff (e.g., OEF/OIF/OND coordinators, etc), and through the community (e.g. grocery stores and shopping centers). In-person recruiting will also be conducted at enrollment and community sites if it is deemed safe to do so in accordance with recommendations for public health and safety. In these cases, one or more research team members will sit at a table/booth in a high visibility area (e.g., a main VA lobby or outside of a grocery store) with a sign indicating that OEF/OIF/OND Veterans are being recruited to participate in a research study. Staff members will provide interested Veterans with a flyer (see Appendix A) about the study. In addition, Veterans interested in participating in the study will be given the option of providing staff members with their contact information so that they can be contacted by phone at a later point in time to complete a telephone screen interview. If a private office is available, as a convenience, participants may be given the option to complete the screening interview in person. We will also place advertisements (Appendix A) in local community-based advertisement sources, on local Craigslist pages, and in other locally-based media platforms, on relevant VA and other Veteran-oriented websites, and social media outlets, pending required approvals from VA public relations office.

We also request permission to conduct periodic queries to recruit new participants using VISTA, VINCI, the Corporate Data Warehouse (CDW), or other approved VA methods for accessing Veteran mailing list information (frequency approximately 2x/year, to be determined based on the number of names generated; i.e. if there are too few or too many names we will adjust the frequency correspondent with staffing so potential participants would not need to wait too long for a research appointment; as the list is exhausted, we will update the list more frequently; maximum number of names generated = 100,000). We will use these VA approved methods to identify Veterans who meet some of our inclusion criteria (e.g. PTSD diagnosis) so that we can reach out to potentially eligible Veterans to let them know that the study is being conducted. An invitation letter will be sent to potentially eligible participants (see Appendix B). Depending on recruitment flow from these letters, we retain the option to attempt to contact potential

participants by telephone after the letter has been sent (allowing at least 1 week for them to receive the letter before calling). If a Veteran says he/she is not interested at any point in this process (e.g., after the first letter or during the follow-up call), their name will be marked on the list and they will not be contacted again. Interested Veterans will complete a telephone screen to determine their eligibility (see Appendix C). This recruitment procedure requires a waiver of consent and waiver of HIPAA authorization (attached). The retrieval of names and addresses to recruit study participants involves no more than minimal risk to subjects and will not adversely affect the rights and welfare of subjects. This waiver is important to successful recruitment of participants as it enables us to reach out to as many Veterans as possible to make participation in the study available to them. The mailing list of contact information generated by the methods detailed above will be stored electronically on the secure VA S:\Research\2. PROJECTS\[name]\MOVED and the VINCI project folder for this study, depending on the required data storage location associated with the approved method of requesting and storing this information. After a Veteran contacts the COE (or we contact the Veteran per above), a brief screening will be conducted by telephone.

6.6 Screening Procedures

The brief screening assessment by telephone will be conducted by a trained psychology technician. The screening assessment (see Appendix C) includes questions regarding inclusion criteria and the administration of self-report questionnaires (MIES & PCL-5). A brief screening assessment should help minimize participant burden, as those who are not eligible will be saved time associated with completing a full baseline assessment. If the Veteran is determined to be ineligible based on the eligibility screening procedure, we will not collect any personally identifying information. For veterans determined to be eligible, we will collect identifying information for the purpose of scheduling a baseline appointment to determine final eligibility. This identifying information will be recorded on an electronic screen registry of initially-eligible participants, including Screen ID#, date of screen, salutation, name, contact information, whether or not it is ok to leave telephone messages (e.g., for appointment reminders), the appointment date/time, enrollment date, and reason not enrolled (e.g., unable to schedule, no longer has time to participate). This information is stored in a password-protected registry on the secure S:\drive (S:\Research\2. PROJECTS\[name]\MOVED). Following the pre-screen (phone screen), for those deemed initially eligible, a cover letter will be mailed to the Veteran in advance of the baseline assessment appointment along with a document that reviews all aspects of participating in the study (i.e., Review of Research Participation), direct deposit form. Coded hardcopy eligibility screening documents will be stored in separate files for those deemed initially eligible versus ineligible. Pre-screen information will be used in aggregate to report the recruitment process (e.g., number screened, number eligible, number ineligible, percentage/reasons for ineligibility, etc). In the event that a Veteran displays a high level of suicidality or reports that they are in crisis during the telephone screen, research staff will assess the risk and consult with an on-site, licensed clinical psychologist or psychiatrist to determine an appropriate course of action. The principal investigator will be notified of any such incidents immediately. The principal investigator will supervise all assessments. Notably, all research staff are trained in suicide prevention and risk assessment.

6.7 Informed Consent Procedures

Veteran Participants: Following the pre-screen, study staff will schedule a baseline assessment appointment to be completed by phone. A copy of the Review of Research Participation Form will be mailed to the Veteran in advance of the baseline appointment for the Veteran to read and consider participation. This procedure will reduce participants' time burden on the day of the assessment, as Veterans will have had the time to read and consider the Review of Research Participation Form prior to the initial baseline appointment. At the start of the appointment, Veterans will be asked if s/he had a chance to read the Review of Research Participation Form, and if not, will be asked to read the form carefully at that time. It should be noted that, regardless of whether or not participants read the Review of Research Participation Form ahead of time, the study staff member will always explain the nature of the study to participants at the beginning of the appointment, as well as the potential risks/benefits of participating in the study. For this study, we will obtain verbal consent, rather than written consent. Verbal consent will only be obtained prior to the baseline assessment and will not be obtained until the researcher is satisfied that the participant has a good understanding of the risks/benefits of participating in the study. All team members with patient contact including consenting procedure will be appropriately trained, assigned duties and documented as per VA regulations

Significant Other Participants: Upon obtaining informed consent from the Veteran participant to allow the study team to initiate contact with the Significant Other (SO), study personnel will call the SO and obtain verbal consent over the phone. This procedure requires a waiver of consent and waiver of HIPAA authorization on behalf of the Significant Other Participant (attached).

6.8 Assessment Schedule

Baseline Assessment: Verbal consent will be obtained at the beginning of the appointment. Following verbal consent, all Veteran participants will complete the baseline assessment. The Veteran baseline assessment is expected to last approximately 40 minutes. This baseline assessment will serve as the final screen to determine full eligibility—indicated by evidence that the Veteran meets all inclusion criteria and does not meet any exclusion criteria. Only after full eligibility is determined will the Veteran be enrolled in the remaining portion of the study and randomized to one of two study conditions.

Upon obtaining verbal consent from the Veteran participant to allow the study team to initiate contact with the Significant Other (SO), study personnel will call the SO and obtain verbal consent over the phone. Once verbal consent is obtained from the SO, the SO will be emailed a web-based link to complete the web-based assessment on Qualtrics, which is HIPAA-compliant and has been approved by the CTVHCS IRB for use in other CoE/ORD-funded studies. The SO baseline assessment is expected to last approximately 35 minutes.

Session Assessments: Veterans will be randomized to either the elevation intervention condition or a no-treatment condition. Both conditions will require Veterans to access a web-based link to Qualtrics twice every week (approximately every Monday and Thursday) for 4 weeks, with 8 sessions in total. For both conditions, Veteran participants will be asked to complete a battery of self-report measures at each session (8 session assessments in total). One session assessment is expected to last approximately 20 minutes.

Follow-up Assessment: Within 1 week of completing the web-bases sessions, Veterans and SOs will be asked to complete a follow-up assessment. The SO will be emailed another web-based link to complete the assessment online using Qualtrics. Veteran participants will be offered the option of completing the assessment online or over the phone. In addition to the follow-up assessment, an audio-recorded qualitative, semi-structured interview will be conducted with Veterans randomized to the elevation intervention condition. The qualitative interview is expected to last approximately 1 hour and will be conducted over the phone.

Figure 1. Participation Timeline

6.9 Measures

All assessment instruments are presented in Table 1. Broadly, assessments were include self-report measures that are valid and reliable.

Table 2. Assessment Instruments							
Measure	Items	Participant	Purpose	Ph screen	BL	Sessions	FU
Moral Injury Events Scale (MIES) ²⁸	9	V	Е				
PTSD Checklist for DSM-5 (PCL-5) ²⁷	20	V	Е				

Beck Depression Inventory-II (BDI-II) 32 20VEMini International Neuropsychiatric Interview (MINI) 30 -VEOhio State Traumatic Brain Injury Identification Method (OSU TBI-ID) 29 -VEDemographic Questionnaire and Military History Expressions of Moral Injury Scale (EMIS-M) 34 17VRCTWorld Health Organization Quality of Life (WHOQOL-BREF) 35 26VRCTPositive and Negative Affective Scale – Short Form (PANAS-SF) 36 10VRCTResponse to Positive Affect Scale (RPA) 38 17VRCTCompassionate Goals (CG)7VRCTProsocialness Scale (PS) 39 16V; SORCTImpact Message Inventory (IMI) 40 59SORCTElevation Scale (ES) 41 13VSA1B
(MINI) ³⁰ Image: Constraint of the state of t
Ohio State Traumatic Brain Injury Identification Method (OSU TBI-ID)29-VEDemographic Questionnaire and Military History Expressions of Moral Injury Scale (EMIS-M)3417VSCExpressions of Moral Injury Scale (EMIS-M)3417VRCTWorld Health Organization Quality of Life (WHOQOL-BREF)3526VRCTPositive and Negative Affective Scale – Short Form (PANAS-SF)3610VRCTPositive and Negative Social Exchanges (PANSE)3724VRCTResponse to Positive Affect Scale (RPA)3817VRCTCompassionate Goals (CG)7VRCT10Prosocialness Scale (PS)3916V; SORCT10Impact Message Inventory (IMI)4059SORCT10
Method (OSU TBI-ID)29Image: Constraint of the systemDemographic Questionnaire and Military History20VSCExpressions of Moral Injury Scale (EMIS-M)3417VRCTWorld Health Organization Quality of Life26VRCT(WHOQOL-BREF)3526VRCT10Positive and Negative Affective Scale – Short10VRCTForm (PANAS-SF)3610VRCT10Positive and Negative Social Exchanges24VRCT(PANSE)37207VRCTResponse to Positive Affect Scale (RPA)3817VRCTCompassionate Goals (CG)7VRCT10Prosocialness Scale (PS)3916V; SORCT10Impact Message Inventory (IMI)4059SORCT10
Demographic Questionnaire and Military History20VSCExpressions of Moral Injury Scale (EMIS-M)3417VRCTWorld Health Organization Quality of Life26VRCT(WHOQOL-BREF)3526VRCTPositive and Negative Affective Scale – Short10VRCTForm (PANAS-SF)3624VRCTPositive and Negative Social Exchanges24VRCT(PANSE)37207VRCTResponse to Positive Affect Scale (RPA)3817VRCTCompassionate Goals (CG)7VRCTProsocialness Scale (PS)3916V; SORCTImpact Message Inventory (IMI)4059SORCT
Expressions of Moral Injury Scale (EMIS-M)3417VRCTImage: Constraint of the state o
World Health Organization Quality of Life (WHOQOL-BREF)3526VRCTPositive and Negative Affective Scale – Short Form (PANAS-SF)3610VRCTPositive and Negative Social Exchanges (PANSE)3724VRCTResponse to Positive Affect Scale (RPA)3817VRCTCompassionate Goals (CG)7VRCTProsocialness Scale (PS)3916V; SORCTImpact Message Inventory (IMI)4059SORCT
Noncention of gamma for Life1010101010(WHOQOL-BREF)3510VRCT10VRCTForm (PANAS-SF)3610VRCT10VRCTPositive and Negative Social Exchanges (PANSE)3724VRCT10Response to Positive Affect Scale (RPA)3817VRCT10Compassionate Goals (CG)7VRCT10Prosocialness Scale (PS)3916V; SORCT10Impact Message Inventory (IMI)4059SORCT10
Positive and Negative Affective Scale – Short10VRCTForm (PANAS-SF) ³⁶ 10VRCTPositive and Negative Social Exchanges24VRCT(PANSE) ³⁷ 24VRCTResponse to Positive Affect Scale (RPA) ³⁸ 17VRCTCompassionate Goals (CG)7VRCTProsocialness Scale (PS) ³⁹ 16V; SORCTImpact Message Inventory (IMI) ⁴⁰ 59SORCT
Form (PANAS-SF) ³⁶ Image: Construction of the state of the
Positive and Negative Social Exchanges (PANSE)3724VRCTResponse to Positive Affect Scale (RPA)3817VRCTCompassionate Goals (CG)7VRCTProsocialness Scale (PS)3916V; SORCTImpact Message Inventory (IMI)4059SORCT
(PANSE)37Image: Construct of the state of the
Response to Positive Affect Scale (RPA)3817VRCTCompassionate Goals (CG)7VRCTProsocialness Scale (PS)3916V; SORCTImpact Message Inventory (IMI)4059SORCT
Compassionate Goals (CG)7VRCTProsocialness Scale (PS)3916V; SORCTImpact Message Inventory (IMI)4059SORCT
Prosocialness Scale (PS)3916V; SORCTImpact Message Inventory (IMI)4059SORCT
Impact Message Inventory (IMI)4059SORCT
Flevation Scale (FS) ⁴¹
Lie valion Scale (LS)
Exercise-Specific Satisfaction Survey (ESSS) 4 V SA1C
Treatment Evaluation Inventory-Short Form 7 V SA1C
(TEI-SF) ⁴²
Client Satisfaction Questionnaire-8 (CSQ-8) ⁴⁴ 8 V SA1C
Ph = Phone; BL = Baseline; FU = Follow-up; V = Veteran; SO = Significant Other; E =
Eligibility; SC = Sample Characteristics; SA = Specific Aim; RCT = Feasibility for use in
future RCT

6.10 Conditions

Following the baseline assessment, Veterans will be randomized to either the elevation intervention condition or a no-treatment condition. Instructions, intervention content for the intervention condition, and session measures for both conditions will be administered online using a web-based link to Qualtrics (see Appendix G), which is HIPAA-compliant and has been approved by the CTVHCS Institutional Review Board (IRB) for use in other CoE/ORD-funded studies.

Elevation Intervention: The intervention will use a spaced, mixed design that includes 2 types of moral elevation exercises: 1) viewing an elevation video (Sessions 1-4); and 2) a recall exercise (Sessions 5-8), which include a brief reflection period wherein the participant journals about their reaction. For Session 1, participants will also be asked to read brief educational materials that will introduce the structure of the intervention, define elevation, and define several virtues (e.g., courage). Defining virtues is expected to help increase participants' awareness and recognition of virtuous acts performed by others, thus increasing the likelihood they will experience elevation throughout the intervention. The primary exercise in Sessions 1-4 will include viewing validated videos¹⁰ (\leq 5 min in length) that elicit elevation. The primary exercise in Session that the participant witnessed a virtuous act and to describe it in detail, with prompts (e.g., What virtue[s]? Who was

involved?). Consistent with positive psychology interventions,⁴³ participants will be instructed to journal about their reaction (~10 min) in all sessions. After the journaling exercise, participants will be presented with a brief goal to be completed prior to the next session that is intended to facilitate greater social engagement. They will report on the completion of that goal in the next session. The goal will be predetermined in Sessions 1-2. Participants will be instructed to generate unique goals for the remaining sessions as it relates to any drives or motivations they may have experienced in response to elevation stimuli (e.g., "After witnessing that virtuous act, what is one action you feel like doing that could be completed before the next session (~20 min). Veterans will be compensated for time spent completing measures at each session.

No-treatment Control Condition: Veterans randomized to the no-treatment condition will access Qualtrics twice per week and complete the same repeated assessments as those in the intervention condition. They will not be exposed to the intervention components (i.e., educational content defining virtues and elevation, viewing videos, recalling elevation-eliciting life events, and journaling exercises).

6.11 Statistical Analysis Plan

Aim 1.A: Assess the feasibility of recruitment, retention, and completion of an 8-session, 1month-long web-based moral elevation intervention.

Analysis Plan: The number and rates of Veterans screened and enrolled versus those retained through 8 sessions and the follow-up assessment will be examined. At all stages, efforts will be made to assess reasons for opting/dropping out to evaluate barriers to participating and feasibility of the proposed methods. The number of sessions completed for Veterans retained through 8 sessions will be examined.

Aim 1.B: Evaluate the ability of the intervention to elicit moral elevation.

Analysis Plan: Scores on the ES will be aggregated across several categories including each session (1-8), session type (video vs. life event recall), and the entire intervention. Mean scores >30, the mid-point of the ES (range=10-50), will be considered to adequately represent medium to high elevation responses to the exercises. We will conduct a visual inspection for trends in mean scores across session numbers and types, and for a signal that ES scores increase over time within each participant (i.e., trajectories across Sessions 1-8).

Aim 1.C: Assess the acceptability of and satisfaction with moral elevation exercises, the intervention's general structure, and the proposed methods.

Analysis Plan: Quantitative measures of acceptability and satisfaction ratings as measured by the TEI-SF and ESSS will be averaged across all participants in the intervention. Mean scores greater than the mid-point of each measure (TEI-SF=18; ESSS=22.5) will be considered trending in support of acceptability and satisfaction. Qualitative interviews will be transcribed. NVivo qualitative software will be used to organize and support coding of data. Methods of the intervention may be adapted immediately based on Veteran feedback if alternative approaches are needed to complete recruitment goals (e.g., retention problems).

Aim 2: Assess the feasibility of randomization to a no-treatment condition and completion of assessments at BL, repeated measures, and FU.

Analysis Plan: The number and rates of Veterans who were randomized to the no-treatment condition and retained through the FU assessment will be examined. The number of repeated measures completed (8 sessions) will also be examined.

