**Title: Pilot Study Testing a Web-Based Moral Elevation Intervention for
Veterans with PTSD and Moral Injury**

ID: D3035-P

NCT: NCT03906240

Principal Investigator: [name].

Statistical Analysis Plan

Date: 06.22.2021

Statistical Analysis Plan

All data management and analyses were conducted with R (R Core Team, 2021). To assess the feasibility and acceptability of MOVED, we calculated descriptive statistics for recruitment and retention data, self-report measures that focused on evaluating components of the intervention, and state elevation scores. For all evaluation measures, the mid-point score for a given measure was used as an indicator for adequate feasibility and acceptability (e.g., average/medium levels of acceptability, or higher). The mid-point score for state elevation was also used as an indicator for feasibility to induce elevation.

Qualitative interviews were transcribed, then coded using an inductive approach by two members of the research team and the first author. Two coders reviewed all transcriptions independently, identified codes based on interview responses, then met to discuss and modify codes. A consensus codebook was established and re-applied to all transcriptions. Emergent themes and subthemes were identified by the first author.

Preliminary examination of outcome measures was conducted via paired samples *t*-tests with the base stats package (`t.test`) and Cohen's *d* effect sizes within each condition with the `rstatix` package (Kassambara, 2021). Assessment of changes in pre-post measures included all participants who were randomized and provided post-session data.

References

- R Core Team. R: A language and environment for statistical computing. R Foundation for Statistical Computing [Internet]. 2021. Available from: <https://www.R-project.org/>
- Kassambara, A. `rstatix`: Pipe-Friendly Framework for Basic Statistical Tests [Internet]. 2021. Available from: <https://cran.r-project.org/web/packages/rstatix>

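### Protocol 6.11 judges the rise in elevation across the eight sessions by eye alone; a within-block slope and a video-to-recall step, each with an interval, should be reported beside the plots

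*Protocol*

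**What the plan says.** Protocol 6.11, Aim 1.B, aggregates ES scores by session, by session type and over the whole intervention. It sets one numerical criterion, which concerns level: "Mean scores >30, the mid-point of the ES (range=10-50), will be considered to adequately represent medium to high elevation responses to the exercises". On change it says "We will conduct a visual inspection for trends in mean scores across session numbers and types", and the same sentence extends the inspection to look "for a signal that ES scores increase over time within each participant". It does not say what counts as such a signal.

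The SAP does not mention session trajectories. It states that "we calculated descriptive statistics for recruitment and retention data, self-report measures that focused on evaluating components of the intervention, and state elevation scores", and then "The mid-point score for state elevation was also used as an indicator for feasibility to induce elevation". Its paired t-tests and Cohen's d apply to outcome measures before and after the sessions: "Assessment of changes in pre-post measures included all participants who were randomized and provided post-session data".

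Three design facts bear on the reading of the plots:
- Protocol 6.2: "The targeted sample size for study completion is 24 Veterans, 12 per group", with 48 randomized to allow for about 50% attrition.
- Protocol 6.8: eight sessions, two a week for four weeks.
- Protocol 6.10: videos fill Sessions 1-4 and recall exercises fill Sessions 5-8.

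**The concern.** A rise judged by eye has no stated uncertainty, and a second analyst cannot be expected to reproduce it. Each Veteran supplies at most eight scores, and about a dozen completers are expected in the intervention arm, so some lines will slope upward by chance and may be described as a signal. The plan also does not say whether session means use everyone who attended that session or completers only. If Veterans with lower usual scores leave first, the plotted mean climbs although nobody has changed. What is at stake is the exploratory statement about change over sessions. The level criterion is not affected.

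**Working it through.** **Inputs from the documents.** 8 sessions; 24 completers, so 24/2 = 12 per group; 48 randomized, so 48/2 = 24 per group if allocation is equal (the ratio is not stated); ES range 10-50. The plan's own figures reproduce: 24/(1 - 0.5) = 48, and the mid-point is (10 + 50)/2 = 30.

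**Assumptions.** The documents give no SD for the ES. I take a within-person residual SD (s) of 4, 6 or 8 points and, unless stated, no true differences in slope between Veterans.

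**1. One Veteran's trajectory.** For sessions 1 to 8 the sum of squared deviations from 4.5 is 42. The SE of the fitted slope is s/√42, and the fitted Session 1-to-8 change is 7 times the slope.
- s = 4: 0.62 per session, 4.3 points over seven steps.
- s = 6: 0.93 per session, 6.5 points.
- s = 8: 1.23 per session, 8.6 points.

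**2. Chance patterns among 12 Veterans with no true trend.** Each fitted slope is positive with probability 1/2. The probability of 7 or more positive slopes is (792 + 495 + 220 + 66 + 12 + 1)/4096 = 1586/4096 = 0.39. For 8 or more it is 794/4096 = 0.19. By simulation, at least one of the 12 shows a fitted rise of 5 points or more with probability 80%, 95% or 98% at s = 4, 6 or 8.

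**3. The mean over 12 complete trajectories.** The 95% half-width of the Session 1-to-8 change is t(0.975, 11) × 7s/√(42 × 12), with t = 2.201. This gives 2.7, 4.1 and 5.5 points. With a true slope SD of 1.0 point per session it becomes 5.2, 6.1 and 7.1 points.

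**4. Drift from attrition.** Suppose 24 Veterans start, 12 finish, and staying correlates r with a Veteran's usual ES level (between-person SD b). The simulated mean of those who stay exceeds the starting mean by about 0.77 × r × b. With r = 0.3 and b = 6 this is 1.4 points; with r = 0.5 and b = 10 it is 3.9 points. There is no within-person change in either case. Both r and b are assumptions.

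**5. Why one slope over Sessions 1-8 is not the remedy.** Let ES be flat within each block and D points higher under recall. The cross-product of centred session number with the step is D(0.5 + 1.5 + 2.5 + 3.5) = 8D, so the fitted slope is 8D/42 per session. The apparent Session 1-to-8 rise is 7 × 8D/42 = 1.33D. A 4-point difference between exercise types would then appear as a 5.3-point rise over time.

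**6. Precision once the step is separated.** Within a block the sum of squares is 2.25 + 0.25 + 0.25 + 2.25 = 5, so two blocks sharing one slope give 10. The SE of the slope grows by √(42/10) = 2.05. For 12 complete trajectories the half-width of the common within-block slope is 2.201 × s/√(10 × 12) = 0.80, 1.21 and 1.61 points per session. The SE of the step for one Veteran is s × √(1/4 + 1/4 + 16/10) = 1.45s. Its half-width over 12 is 2.201 × 1.45s/√12, or about 3.7, 5.5 and 7.4 points.

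**The case against.** The strongest reply is that this is a feasibility pilot and the trend decides nothing. Much of that stands. Aim 1.B asks whether the intervention can elicit elevation, which is a question of level. Its only criterion is the mean above 30, which the SAP repeats as a mid-point indicator. The alternative strategies in Protocol 6.12 respond to elevation that is too low, not to a flat trajectory. A reader might infer that the Aim 1.B conclusion rests on visual judgement; the documents do not support that.

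A reader might also infer that a rise of 3 to 5 points in the group mean is indistinguishable from noise. Step 3 does not support this across the assumed range. At s = 4 the half-width is 2.7, so the whole range lies outside it, and at s = 6 (half-width 4.1) a 5-point rise does too. Those figures assume no slope differences, and they use 12 Veterans. If all 24 in the arm supplied all eight scores, the half-widths would be 1.8, 2.7 and 3.6. The noise argument is secure for single trajectories only.

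Nor do the documents show that a future trial would be planned on an ES slope. Table 2 in Protocol 6.9 assigns the ES to Aim 1.B and marks other measures for use in a future RCT. The 39% and 19% figures describe a count of rising lines, and the plan does not propose such a count as a rule.

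Finally, inspection by session type can reveal a step between video and recall that a single fitted slope would hide. That is a good reason to keep the plots. It does not answer the absence of any estimate, since the SAP already quantifies change in its pre-post measures within the same small arms.

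**Conclusion.** The point holds as a modest improvement to an exploratory analysis. The plan looks for a rise within each participant with a method that cannot separate it from noise: the standard error of one Veteran's fitted change is 4.3 to 8.6 points on a scale running from 10 to 50. Session means may in addition drift by about 1.4 to 3.9 points through selective dropout. These sizes rest on assumed SDs and correlations. The 39% figure needs only independent trajectories with errors symmetric about no trend. The level criterion and the feasibility conclusions are untouched.

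**What to change.** Keep the plots. Add to Protocol 6.11 and the SAP a linear mixed model of ES in the intervention arm that uses every available session score, including those of Veterans who stop early. Include a random intercept per Veteran (and a random slope if the model converges), session number, and a step for Sessions 1-4 versus 5-8. Estimating separate slopes within each block is an acceptable alternative. Report the within-block mean slope per session and the video-to-recall step, each with a 95% CI, as descriptive estimates without a significance test. State that a single Session 1-8 slope will not be read as change over time.

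The cost is a sentence or two in each document and a few lines of R, with no new data. There are three drawbacks:
- Separating the step from time roughly doubles the slope's standard error, so with about 12 completers the intervals will be wide.
- The SD of individual slopes may not be estimable. If the random slope is dropped while Veterans truly differ in slope, the interval for the mean slope will be too narrow, and the report should say so.
- The model deals with attrition only to the extent that dropout depends on scores already observed.
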